## **Introduction:**

Globally, pneumonia is considered one of the prominent causes of children's morbidity and mortality, particularly in developing countries, causing 29% of the under-Five mortality(1).

According to the World health organization estimates, 66% of deaths due to pneumonia occur in infancy, where 90% occur in developing countries(2).

In Egypt, according to UNICEF 2018, Acute Respiratory Tract Infection (ARTIs)was estimated to account for 11% and 19% of the under-five and post-neonatal mortalities respectively(3).

Despite the well-recognized role of vitamin D in metabolism and homeostasis in the general population, there is now growing interest in its probable association with pneumonia(4).

Basically, 25(OH) D and 1,25 (OH)2D are surrogate markers of the active form of vitamin D in the body. Recently, it has been highlighted that Vit D(1,25(OH)2D ) has a crucial role in host defenses, inflammation, and immunity. Furthermore, Vit D (1,25(OH)2D ) promotes the expression of cathelicidin and B-defensin (antimicrobial peptides) that are broadly expressed in the body and play a vital role in innate immunity as a result of their chemotactic action and toxin neutralization(5).

Due to its short half-life (12-36 hours) compared to 25(OH)D (3 weeks), 1,25(OH)2D is proposed to provide a more valid measure for better prediction of the vitamin D role in reducing the severity and improving the prognosis of patients with (ARTIs)(6).

Globally, about 30% to 90% of Under-5 children experience vitamin D deficiency. This could vary among children, according to the socioeconomic, environmental and behavioral circumstances.

Studies evaluating the association of 1,25 (OH)2D deficiency and the severity of respiratory tract infection, are rare and showed controversial findings(7,8).

However, an Indian systematic review polled the results of 12 studies, with 2279 participants, highlighted the significant correlation between vitamin D deficiency and incidence and severity of ALRIs(9).

A prospective cohort study conducted in Yemen in 2009, examined the ability of deficient levels of vit.D to predict the outcomes of severe pneumonia. The study documented the significant association between vitamin D deficiency with neutropenia and hypoxia in patients with severe pneumonia, thus predicting poor prognosis(10).

In Egypt 2010, a case-control study conducted on children aged 2 to 5 years to examine the impact of vitamin D deficiency on the susceptibility of pneumonia. The study illustrated that Vitamin D deficiency is associated with a higher incidence and more severe pneumonia(11).

Hashemian H., et al 2017, advocated providing children(particularly suffering from pneumonia) with adequate amounts of vitamin D supplements(12).

Nevertheless, few studies have been conducted to evaluate the impact of vitamin D supplementation on the outcome of pneumonic infants.

Thus, we urge to conduct a randomized controlled trial (RCT) in Abou ElReesh tertiary Pediatric hospital, to evaluate the effects of vitamin D3 supplementation to children with pneumonia. We postulated that supplementation of 100 000 IU of vitamin D3 (Cholecalciferol) will reduce the duration of illness in those children and improve their outcome.

### **Subjects and Methods:**

#### **Study design and study setting**

The current study is a randomized, double-blinded placebo-controlled trial (RCT) that was conducted in Cairo University Abou ElReesh Children hospital, which is a university-affiliated teaching hospital in Egypt, to evaluate the effect of vitamin D3 supplementation on the outcome of treatment of children with pneumonia. Pneumonia cases were recruited from two of the hospital general pediatric departments and the four pediatric intensive care units (PICUs) of the hospital.

#### **Sample Size and study population**

To detect a 20% difference in the mean duration of pneumonia between the vitamin D arm and control arm [5 days vs. 6 days (SD 2)] allowing Type I error of 5% and Type II error of 10%, 86 per group (172 total) is the minimum number to be recruited [13]. After allowing for 10% for nonresponse or loss for follow-up and 25% for exclusion of children diagnosed with sufficient or toxic level of vitamin D after vitamin D testing (Box 1) according to prevalence of vitamin deficiency in a pediatric hospital of eastern India [14], 233 was the minimum number to start with. Mild and moderate pneumonia cases were recruited from two of the hospital general pediatric departments chosen by simple random sample from a total of six hospital departments while severe pneumonia cases were recruited from the four PICUs of the hospital.

All children (259 children) between 1 month and 12 years of age admitted to the selected departments during the period from 9th September 2019 to 15th December 2019 and diagnosed clinically with pneumonia according to World Health Organization criteria of severity [15] (Box 2) were screened for the inclusion criteria. Children who had clinical signs of rickets (2 children), severe illnesses (meningitis, heart or renal disorders, measles, severe malnutrition, endocrine dysfunction, hypercalcemia, hyperthyroidism, and suspected tuberculosis) (4 children) or were known to have received high-dose vitamin D treatment in the past 3 months (3 children) were excluded from the study. Children with sufficient (52 children) or toxic (7 children) levels of vitamin D were also excluded.

Thus, 191 child (93 in the intervention arm and 98 in the control arm) who had pneumonia with insufficient or deficient level of vitamin D and their parents consented to participate were actually enrolled in the study, completed the baseline and the outcome assessments and continued the daily clinical follow up till their discharge (improvement or death) from the hospital.

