### **Outcomes assessment**

Outcomes were assessed 7 days after vitamin D injection, the first day whereas vitamin D reaches its maximum level in the blood [19] to guarantee the assessment of all participants before their

discharge. The primary outcome variables were changed in serum level of 25(OH)D, PaO2/FIO2, serum creatinine, C reactive protein, and serum bilirubin levels and platelets count. Also, the SOFA score for severe cases. The secondary outcomes included the fate of the cases (improvement or death) and the duration between enrolment and hospital discharge for improved cases.

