#### **Statistical analysis:**

Patients' percent change of Vitamin D (25 (OH)2D) was calculated to quantify the change levels before and after vitamin D3 (Cholecalciferol) administration through the equation:

Pediatric, Blood Vitamin D level (BVD) %change =

$$[(\text{BVD after} - \text{BVD before}) \div \text{BVD before}] \times 100$$

Collected data were entered and analyzed using the Statistical Package for Social Science Software (SPSS) program, version 21.0 IBM. Tests of normality of data (like Shapero-Wilk test) revealed that data isn't normally distributed. That's why non-parametric tests like MannWhitney and Kruskal-Wallis tests were used in univariable comparisons to quantify the associations of continuous variables. Data were summarized using the median and interquartile range for quantitative variables. Spearman correlation test was used to detect the relationship between continuous variables. P values below 0.05 were considered statistically significant. A multivariate Cox regression analysis model was conducted to explore the independent effect of vitamin D3 supplementation on the overall survival of pneumonic children.

Given the short period of the study follow-up and single intervention, there was no stopping rule or interim analyses.

All children randomized were included in the analysis on an intention-to-treat basis unless the outcome measures were missing (n = 0) or reported to have recovered or lost within 24 h (n = 0). Meantime to recovery for the episode of pneumonia at recruitment was compared for the vitamin D group and control group. Kaplan-Meier plots and log-rank tests were used to compare the time to recover from the index episode of pneumonia between the vitamin D and placebo groups.

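### The planned starting number of 233 does not retain the stated 172 children under the plan's own 10% and 25% losses; 255 (or 265) would be needed

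*Combined protocol and SAP*

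**What the plan says.** All the figures are in the combined protocol and SAP, mainly in the section Sample Size and study population.

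- The target is a difference in mean pneumonia duration of 5 against 6 days with SD 2, a Type I error of 5% and a Type II error of 10%. The result is "86 per group (172 total) is the minimum number to be recruited".
- The target is then inflated: "After allowing for 10% for nonresponse or loss for follow-up and 25% for exclusion of children" who are "diagnosed with sufficient or toxic level of vitamin D after vitamin D testing". The 25% is tied to a published prevalence of vitamin D deficiency in a paediatric hospital.
- The result is that "233 was the minimum number to start with". No formula is given.
- The same section reports what happened: 259 children were screened, 9 were excluded on clinical or prior-treatment grounds, 59 were excluded for sufficient or toxic vitamin D, and the trial enrolled "191 child (93 in the intervention arm and 98 in the control arm"). All of them are said to have completed the baseline and outcome assessments.

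**The concern.** A starting number has to be large enough that the target remains after the expected losses. The 25% is the share of tested children expected to be ineligible, so it applies to the larger group that is tested and not to the 172 who remain. Adding 10% and 25% of 172 to 172 uses the wrong denominator and gives too small a start.

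At stake is whether the planning statement is consistent with itself. As written, it tells the reader that starting with 233 secures 172 children and a 10% Type II error under the stated losses. Anyone who reuses 233, or the method behind it, would plan too few children.

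**Working it through.** **Inputs** (Sample Size and study population): difference 1 day, SD 2, Type I error 5%, Type II error 10%, 86 per group (172 total), losses 10% and 25%, starting number 233.

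**Step 1. Reproduce the 172.** For two means, n per group = 2 x (1.960 + 1.282)^2 x 2^2 / 1^2 = 84.1, so 85 by the normal approximation. The t-test solution is 85.03, so 86. The plan's 86 is reproduced with a two-sided 5% test. Sidedness is not stated, but a one-sided test needs 69.2, so 70, and 86 therefore fits two-sided only.

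**Step 2. Reproduce the 233.** Simple routes from 172:

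| Route | Result |
|---|---|
| 172 x (1 + 0.10 + 0.25) | 232.2, rounded up to 233 |
| 172 x 1.10 x 1.25 | 236.5, rounded up to 237 |
| 172 / 0.75 (omits the 10%) | 229.3, rounded up to 230 |
| 172 / (0.90 x 0.75) | 254.8, rounded up to 255 |
| 172 / (1 - 0.35) | 264.6, rounded up to 265 |

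Only the additive mark-up gives 233. A base of 170 with compounded mark-ups gives 170 x 1.10 x 1.25 = 233.75, but this reaches 233 only by rounding down, and 170 is not the plan's stated base.

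**Step 3. What 233 leaves.**

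- Losses in sequence: 233 x 0.90 x 0.75 = 157.3, about 157 children, which is 172 - 157 = 15 short.
- Both losses as shares of the starting number: 233 x 0.65 = 151.5, about 151 children, which is 172 - 151 = 21 short.

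Two checks do not depend on how the losses combine. First, 233 x 0.75 = 174.75, so the vitamin D exclusion alone leaves a margin of 2.75 children (2.75 / 174.75 = 1.6%) for an allowance set at 10%. Second, 233 can absorb a total loss of at most 1 - 172/233 = 26.2%, whereas the planned losses total 1 - 0.675 = 32.5% or 35%.

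**Step 4. Planned power** (noncentral t, 1 day, SD 2, two-sided 5%).

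| Children per arm | Power | Type II error |
|---|---|---|
| 86 / 86 (stated target) | 90.3% | 9.7% |
| 78 / 79 (sequence) | 87.6% | 12.4% |
| 75 / 76 (both shares of start) | 86.3% | 13.7% |

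**Step 5. Starting number needed.** In sequence, 255 (check: 255 x 0.675 = 172.1), which is 22 more than 233. With both as shares of the start, 265, which is 32 more.

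**Step 6. What was enrolled.** 259 - (2 + 4 + 3) - (52 + 7) = 191, above 172.

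**The case against.** The strongest objection is that nothing followed from the error. The document is written after recruitment closed, 191 children were enrolled against a minimum of 172, and the Statistical analysis section includes every randomized child "unless the outcome measures were missing (n = 0"). This stands, and it limits the point to the planning text. It does not make 233 the right minimum.

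A second objection is that allowing for 10% and 25% can be read as a plain mark-up on 172, in which case 233 is computed as intended. That is probably how the figure arose. It does not rescue it: the 25% rests on a prevalence, which is a share of children tested, and no reading of the percentages as shares of the children lost lets 233 yield 172. The shortfall also holds whatever route led to 233.

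A third objection is that the plan never says the losses apply in sequence. That is right, so no single set of corrected figures can be given without the condition attached. On the other reading the gap is larger.

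A fourth is that the power figures describe a comparison of two means, while the Statistical analysis section uses Mann-Whitney and log-rank tests and Outcomes assessment makes the duration a secondary outcome. This also stands: the figures measure the planning statement against its own assumptions and nothing more.

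Three further inferences are tempting, and the documents support none of them:

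- *That the trial recruited too few children.* It did not: 191 exceeds 172.
- *That screening 259 children covered the corrected requirement because 259 exceeds 255.* Nine of the 259 left for reasons that neither allowance covers. On the remaining 250, 250 x 0.675 = 168.75, below 172. On the other reading, 259 is below 265. The reassurance comes from the 191 enrolled, not from the number screened.
- *That 172 was therefore met for the duration comparison.* Outcomes assessment states: "The secondary outcomes included the fate of the cases (improvement or death) and the duration between enrolment and hospital discharge for improved cases". The document does not give the number of deaths, so the number of children contributing a duration is not known.

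**Conclusion.** The point holds, with minor severity. The starting number of 233 supports neither the stated 172 nor the stated 10% Type II error under the plan's own loss rates. Planned power for the two-mean comparison falls about 2 to 4 points below 90%, depending on how the two losses combine.

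This rests on a 1-day difference, SD 2, a two-sided 5% test (not stated, but the only version that fits 86 per group) and equal allocation. The additive origin of 233 is inferred from the match and needs the sponsor's confirmation; the shortfall itself does not depend on it. The error lies in the planning statement only, and the recruitment minimum of 172 was exceeded.

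**What to change.** Keep 233 as the historical planning figure. The sponsor should state how it was derived, confirm that the 5% level is two-sided, and add to the sample-size section:

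> Under the planned losses of 10% and 25%, 233 corresponds to about 157 children and about 88% power on the planning two-mean comparison if the losses apply in sequence (about 151 and 86% if both are shares of the starting number); 255 (or 265) would have been needed to retain 172. In the event, 191 children were enrolled and completed outcome assessment, above the recruitment minimum of 172.

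Once the sponsor confirms how the two percentages were meant, the set that does not apply can be deleted. The addition should not compare the 259 screened with 255, should not claim that 172 was met for the duration comparison, and should not give a power figure for the 191 enrolled.

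The cost is two sentences, a short clarification from the sponsor and a slightly less favourable planning figure. No data, enrolment or analysis changes.

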**Box 1: Level of vitamin D [16]**

Sufficient vitamin D (25(OH)D:  $\geq 30$  ng/mL),

Insufficient vitamin D (25(OH)D or at risk of deficiency : 10-29 ng/mL), and

Deficient vitamin D (25(OH)D:  $<10$  ng/ mL).

**Box 2: Diagnosis of Pneumonia [15]**

**Pneumonia:** (i) Age-specific tachypnoea ( $>60$  / min if  $<2$  months;  $>50$  / min if 2–11 months;  $>40$  if 12–24 months) and (ii) absence of wheeze (with or without fever).

Fever: Axillary temperature  $>37.50$  °C (age 1 week– 3 months) or  $>38.0$  °C (2–23 months).

Axillary temperature was measured using a standard mercury thermometers

Respiratory rate was measured twice for one full minute while the child is quiet using stopwatches taking the average count.

**Mild pneumonia:** Minimally increased work of breathing, no hypoxemia, able to tolerate PO

**Moderate pneumonia:** Hypoxemia, inability to tolerate **PO**, **moderately** increased work of breathing (grunting, retracting, tachypnea).

**Severe Pneumonia:** Significantly increased work of breathing, altered mental state, concern for respiratory failure sepsis, failure to maintain oxygen saturation with FiO2 of 50%, need for positive pressure ventilation. Oxygen saturation was measured using a pulse oximeter with a probe on a finger or toe, in room air.

**Improvement (discharge criteria):** (Meets all) tolerating PO, not hypoxic ( $> 90\%$ ), mildly increase or normal work of breathing [17].

**Vitamin D testing**

Two milliliters of venous blood was collected on plain tubes, left for 10 min to clot and then centrifuged at 3000 rpm for 5 min; the separated serum samples were stored at -20 °C till the time of assay and used for detection of concentrations of serum 25OH Vitamin D Total ( 25OH Vitamin D2 and D3) by ELISA using (DIAsource 25OH Vitamin D Total ELISA Kit, Catalogue No. KAP 1971) supplied by DIA source Immunoassays S.A. ([name] ), according to the manufacturer's instructions and based on the principle of solid-phase Enzyme-Linked Immunosorbent Assay performed on microtiter plates. The amount of substrate turnover is determined colourimetrically by measuring the absorbance, which is inversely proportional to the total 25OH Vitamin D (D2 and D3) concentration. A calibration curve is plotted and the total 25OH Vitamin D (D2 and D3) concentrations of the samples are determined by dose interpolation from the calibration curve.

**Random allocation of study groups**

The children were individually randomized into intervention or control groups using a random number sequence elicited in an Excel spreadsheet with no limitations. The allocation was further hidden by using closed dark envelopes. A biostatistician and an office secretary who were not members of the investigating team did independently the randomization, repackaging, sequencing, and allocation concealment. None of the study staff and participants' parents was aware of the drug or placebo being dispensed. The codes were revealed only at the time of final data analysis.

The children were followed clinically on a daily base by the three study pediatricians to assess the resolution or deterioration of signs and symptoms of pneumonia till being discharged from the hospital whether due to recovery or death. The routine treatment of inpatient children is free of charge in Abou ElReesh Children's hospital, while vitamin D was paid by the researchers to be given free of charge to the children in the intervention arm during the study period.

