### **Baseline assessment**

Data was collected for each participant regarding socio-demographic variables (age, sex, feeding practices), skin color, nature and duration of presenting symptoms. All children were examined for vital signs (temperature, heart rate, respiratory rate, blood pressure, oxygen saturation), pallor, cyanosis, nasal flaring, grunt, and mental status. Pa O2/FIO2 was measured and serum creatinine, C reactive protein, platelet count and serum bilirubin laboratory tests were done. SOFA score was assessed for severe pneumonia cases.

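### Neither the allocation nor any stated analysis uses the ward/PICU entry stream, so precision is lost and severity balance is left to chance

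*Combined protocol and SAP*

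**What the plan says.** The section *Random allocation of study groups* describes individual randomisation "using a random number sequence elicited in an Excel spreadsheet with no limitations", with sealed envelopes and outside staff handling the codes. No blocking, stratification or minimisation appears there or elsewhere.

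Under *Sample Size and study population*, "Mild and moderate pneumonia cases were recruited from two of the hospital general pediatric departments", while "severe pneumonia cases were recruited from the four PICUs of the hospital". Entry stream and severity class are therefore the same variable, known before a child is allocated. The same section reports enrolment as complete, with "191 child (93 in the intervention arm and 98 in the control arm".

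Box 2 defines severe pneumonia by features such as concern for respiratory failure and need for positive pressure ventilation. It defines improvement by absence of hypoxia, oral tolerance and near-normal work of breathing.

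*Statistical analysis* names Mann-Whitney and Kruskal-Wallis tests, Kaplan-Meier plots with log-rank tests for recovery time, and a multivariate Cox model for overall survival. None of the tests is described as stratified by severity, and the Cox covariates are not listed.

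**The concern.** A child who enters through a PICU starts further from the discharge criteria in Box 2 than a ward child and, on the same definitions, is at higher risk of death. The plan does not use the term prognostic factor, but the inference from its own definitions is strong.

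If neither the allocation nor the analysis uses this variable, two things follow. The arms may differ by chance in their share of severe cases, and nothing stated in the analysis would take account of that. The variation between ward and PICU children also stays in the error term of every comparison, although it could be removed at almost no cost. At stake is the precision of the recovery-time comparison on which the trial was sized, and of the marker and mortality comparisons.

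**Working it through.** **The plan's own sample size.** The inputs, from *Sample Size and study population*, are 5 against 6 days, SD 2, type I error 5% and type II error 10%.

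- Normal formula, two-sided: n = 2 × [2 × (1.960 + 1.282) / 1]² ≈ 84.06, so 85 per arm.
- The t-based version gives 85.03, which rounds up to the stated 86 per arm (172 in all).

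The figure reproduces, and the point does not depend on it. The SD of 2 days is carried forward below as the overall SD of stay across both streams.

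**Chance imbalance.** The arms are 93 and 98. The plan does not give the severe share, so 20 to 50% is assumed. With S severe children among 191, the number in the arm of 93 is hypergeometric. The table gives the probability that the severe shares of the two arms differ by 10 percentage points or more.

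| Assumed severe share | S | Probability |
|---|---|---|
| 20% | 38 | 0.069 |
| 30% | 57 | 0.114 |
| 40% | 76 | 0.183 |
| 50% | 96 | 0.149 |

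With an assumed 2-day longer stay in severe cases, a 10-point imbalance moves the difference in mean stay by 0.10 × 2 = 0.2 day, against a planned effect of 1 day.

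**Precision.** The planned standard error at 93 and 98 is 2 × √(1/93 + 1/98) = 2 × 0.1448 = 0.29 day. With a gap of D days between severity classes and a severe share p, the between-class variance is p(1 − p)D². For D = 2, out of a planned total variance of 2² = 4:

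| p | Between-class variance | Share of 4 | Within-class SD | Standard error (× 0.1448) |
|---|---|---|---|---|
| 0.2 | 0.64 | 16% | 1.83 | 0.27 |
| 0.3 | 0.84 | 21% | 1.78 | 0.26 |
| 0.4 | 0.96 | 24% | 1.74 | 0.25 |
| 0.5 | 1.00 | 25% | 1.73 | 0.25 |

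The standard error falls by 1 − √0.84 = 8% to 1 − √0.75 = 13%.

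**Upper limit on the assumed gap.** With D = 4, the between-class SD is 4√[p(1 − p)] = 1.60, 1.83, 1.96 and 2.00 days at the four shares. The within-class SD is √[4 − 16p(1 − p)] = 1.20, 0.80, 0.40 and 0. At shares of 40 to 50% this would use up nearly all of the planned SD, so a 4-day gap does not fit the plan's own figure there.

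**Large shifts.** At D = 2, a shift of 0.5 day needs a 25-point imbalance. Its hypergeometric probability is below 0.1% at every assumed share.

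**The case against.** The strongest reply is that simple randomisation is valid. The log-rank and Mann-Whitney tests already allow for chance imbalance, so an uneven split of PICU children is part of the stated type I error and not an extra hazard. That stands. What remains is a loss of precision.

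A reader might infer that chance imbalance could readily mimic or hide the 1-day effect. The documents do not support this. It would take a stay difference of about 4 days between severity classes, which at the higher severe shares leaves almost no variation within a class under the planned SD. At a 2-day gap, a shift of even half the planned effect is very unlikely.

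A reader might also infer that the SOFA comparison is compromised, because SOFA is listed among the primary variables for severe cases only ("Also, the SOFA score for severe cases"). Within that subset the comparison is still randomised, so ward/PICU confounding cannot arise. The only cost is unequal numbers, and a 60:40 split keeps 4 × 0.6 × 0.4 = 96% of the information of an even one.

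Two further points stand in part. Change from baseline removes some of any initial difference in the markers, but not differences in their course. The Cox model may include severity, but the plan does not say so, and that model concerns survival and not recovery time. Finally, enrolment is reported as complete, so a remedy confined to the allocation list would come too late.

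**Conclusion.** The point holds as a design and analysis weakness of moderate size, not as an error or a source of bias. The plan knows each child's severity class before randomisation and uses it neither in the allocation nor in any stated test.

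The chance of a 10-point or larger difference in severe share is about 7 to 18%. The precision forgone on mean stay is about 8 to 13% of the standard error (0.29 against 0.25–0.27 day).

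These figures rest on two assumptions that the documents do not supply: a severe share of 20 to 50%, and a stay 2 days longer in severe cases. They also take the planned SD of 2 to apply to stay across both streams. A smaller gap would shrink the gain. The standard-error figures describe a comparison of means; the gain for the log-rank and rank tests will not match them exactly.

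**What to change.** In *Statistical analysis*:

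- Stratify the log-rank test for recovery time by entry stream (ward or PICU).
- Use a severity-stratified rank test (van Elteren) for duration and for the marker changes measured in both streams. SOFA, measured in severe cases only, needs no such stratum.
- Name the Cox covariates and include severity among them.
- Report severity by arm in the baseline table.
- If the codes were already open when these analyses were chosen, say so.

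If allocation can still be changed, or for any repeat of the design, replace the single list in *Random allocation of study groups* with permuted blocks of randomly varying size within the two entry streams. For a trial already enrolled, that section should continue to describe what was done. Stratified allocation is not enough alone: followed by unstratified tests, it would improve balance without narrowing the error bars. The analysis must use the stratum too.

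The cost is slightly more analysis work and, where allocation changes, two lists and two syringe sequences instead of one. Random block sizes and the existing outside allocation staff keep predictability low.
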